
關鍵詞 (Keywords) : COVID-19, Long COVID, long-term effects, mixed-methods, health-related quality of life, longitudinal cohort study

Aims

The overarching goal of this proposed project is to explore the Long COVID and associating factors in Taiwan. In the proposed research project, we intend to investigate both ongoing and post-COVID-19 syndrome defined by NICE guideline and referred these symptoms as Long COVID. Building upon the overarching goal, the specific aims of this research project are to (1) integrate the state of science of Long COVID, (2) describe the changes of various symptoms and HRQOL after 3, 6, 9, and 12 months of COVID-19 diagnosis, (3) explore predicting factors of the existence and severity of Long COVID, and (4) explore how patient experienced COVID-19 symptoms.

Introduction

Starting from the beginning of 2020, the COVID-19 pandemic has already affected more than one billion people with over three million deaths globally [1]. In Taiwan, about ten thousands covid-19 cases were confirmed in mid-June, 2021, and the case number continues to grow [2]. While a lot of individuals diagnosed with COVID-19 completed the treatment course of the acute phase and returned to their community, a considerable portion of COVID-19 survivors continuously experienced complicated, distressing, and multiple long-term symptoms weeks to months after COVID-19 diagnosis [3, 4]. These long-term symptoms sometimes may be labeled as Long COVID, post-COVID symptoms, or ongoing symptoms and have profound impact on individuals health, function, and quality of life [5, 6]. Thus developed guidelines stress the importance of monitoring and managing Long COVID continuously [7]. However, the symptom profile is still vague and the guideline is left to be scrutinized.

Symptom profile of Long COVID

Although it is expected that the acute symptoms of COVID-19 last about a week [8], researchers have warned that more than 50 long-term symptoms or signs can be experienced by COVID-19 survivors weeks after diagnosis [3].

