These evidence of long-term organ damage, symptom burden, and functional impairment lead healthcare providers to wonder if it is possible to predict who will develop Long COVID. While results from some studies showed that the severity of acute COVID-19 symptoms associate with Long COVID [6, 15], a study pointed out that there is no relationship between disease severity and chronic fatigue post COVID recovery [9]. Instead, female and history of psychological distress may associate with prolonged fatigue [9]. Another study recruited more than four thousand patients in UK found that older age, increasing BMI, female sex, and experiencing more than five symptoms during the first week of illness were associated with Long COVID [16]. In a similar vein, female sex and overweight/obesity were found to be related to lower HRQOL in survivors [13]. In short, the severity of acute symptoms, preexisting comorbidity, female gender, and BMI or weight are all potential predictors of Long COVID [6, 9, 13, 15, 16]. With that being said, current evidence is premature to determine what can predict the existence or severity of Long COVID at different stage of survivorship.

-Guideline for Current Practice

In order to managing Long COVID, National Institute for Health and Care Excellence (NICE), the Scottish Intercollegiate Guidelines Network (SIGN), and the Royal College of General Practitioners (RCGP) published a rapid guideline in December, 2020 [17]. In this NICE guideline, symptoms of COVID-19 are categorized as acute (i.e., signs and symptoms for up to 4 weeks), ongoing (i.e., signs

and symptoms from 4 to 12 weeks), and post-COVID-19 syndrome (i.e., signs and symptoms continue for more than 12 weeks and are not explained by an alternative diagnosis). It recommends that healthcare providers should be aware of possible symptoms, actively discuss with survivors in terms of their symptom experience and how symptoms affect their function and life, offer chest X-ray by 12 weeks after acute COVID-19, offer an exercise tolerance test, and consider referring survivors to an integrated multidisciplinary assessment. It also stressed the importance of long-term follow-up with symptom changes. However, upon the time of guideline development, accessible evidence was still scarce and of poor quality [7]. Furthermore, while the guideline repeatedly mentioned the needs to discuss symptom impacts on function and life, relevant reference is even less available.

The Knowledge Gap

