1. Number of study phases, type of implementation process, and stage of integration of approaches: The proposed project include three phases. Following the first phase of preparation, **phase two (quantitative strand) and three (qualitative strand) are conducted concurrently**. The integration of quantitative and qualitative findings happens in the end of the whole projects to triangulate qualitative and quantitative findings.
2. Theoretical perspective: The embedded design includes dealing with both quantitative and qualitative data and is supported by the pragmatism worldview. The pragmatism perspective appreciates both singular and multiple realities and emphasizes practicality. Pragmatism embraces abduitive logic and is research question centered [20].
3. Function of the research study: The embedded design allow us to enhance the overall design of the quantitative, cohort study by adding qualitative approach. It is an important strategy as the interested phenomenon is not clearly understood and may be missed if we only use quantitative methods to explore.
4. Priority of methodological approach: Quantitative method is the primary part of this study.

Study procedure

In the first phase, a systematical review will be conducted to address research aim one. The second and third phase will cover quantitative strand and qualitative strand, respectively. The quantitative strand will employ cohort study design to follow up with COVID-19 survivors regularly for a year (aim 2 and 3). The qualitative design will explore their symptom experience (aim 4).

-Phase two: Quantitative strand

The independent variables for the cohort study of the quantitative strand are demographic variables (e.g., age, sex, chronic disease, smoking, BMI) and symptom severity at COVID-19 diagnosis. The dependent variables are existence and severity of Long COVID symptoms and several indicators of health status, including known infection episodes, fever, SpO₂ level, hospital or emergency room admissions, and any new diagnosis.

[figure not shown]

Figure 1. Two Phases Mixed Methods Research Design

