Sampling and Recruitments. Inclusion criteria are individuals who are (1) at least 20 years-old and (2) diagnosed with COVID-19 within six months. Exclusion criteria are individuals who (1) are still in the active phase of COVID-19 infection (i.e., diagnosed within 4 weeks) and (2) have cognitive impairment or other issues that prevents them from doing self-ratings of symptoms via phone interviews. The estimated sample size is about 98 subjects based on G*Power 3.1.9.4 calculation (effect size $f^2=0.15$, $\alpha=0.05$, $\beta=0.2$, 6 predictors). Considering the loss of follow-up rate of 20%, 118 subjects are needed.

Potential subjects will be identified through the following strategies: (1) searching the intranet of participating medical institutions (e.g., National Taiwan University Hospital, National Yang Ming Chiao Tung University Hospital and Min-Sheng General Hospital), (2) recruitment messages posting on social media, and (3) referrals from collaborating healthcare providers. After participants fill out the online questionnaire, research assistant will approach potential subjects via phone to explain the research, explore their willingness, and screen for eligibility. Individuals who are eligible and agree to participate in the study will receive documents of study information and consent form by mail. Participants are required to mail back the signed inform consents.

Upon the receiving the signed inform consents, the subjects will be followed immediately to confirm participation and collect demographic data. They will then be regular followed up at 3 (for those who are participated within 3 months of COVID diagnosis), 6, 9, and 12 months (T1-4) from the diagnosis of COVID-19. During these regular follow-ups, subjects will need to report health status indicators and rate their symptom severity and HRQOL based on selected instruments. Subjects will have access to a line group managed by the research team. They can communicate with the research team regarding any issues of research or symptoms through line group. All data collection will be occurred via online questionnaire, phone or video call interview (e.g., +Google meet or line video call). Paper documents, such as inform consents, will be stored in the locked cabin located at National Taiwan University School of Nursing. Electrical data will be managed and stored using Redcap and encrypted Dropbox.

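### The acute phase is excluded at entry, but no rule keeps ratings taken soon after a new COVID-19 infection out of the aim 2 and aim 3 analyses of Long COVID

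*Combined protocol and SAP*

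**What the plan says.** All references are to the combined protocol and SAP.

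- **Definition.** Under Aims, the authors write that "we intend to investigate both ongoing and post-COVID-19 syndrome defined by NICE guideline". The guideline section gives the first category as "acute (i.e., signs and symptoms for up to 4 weeks" and the last, post-COVID-19 syndrome, as "signs and symptoms continue for more than 12 weeks and are not explained by an alternative diagnosis".
- **Entry.** Under Sampling and Recruitments, participants must have been "diagnosed with COVID-19 within six months", and those who "are still in the active phase of COVID-19 infection (i.e., diagnosed within 4 weeks" are excluded.
- **Follow-up.** Visits are at 3 months (only for those who join early enough) and then at "6, 9, and 12 months (T1-4) from the diagnosis of COVID-19". At each one, "subjects will need to report health status indicators and rate their symptom severity and HRQOL based on selected instruments".
- **Infection episodes.** The quantitative strand lists, among its dependent variables, "several indicators of health status, including known infection episodes, fever" and others. They have no other role in the plan.
- **Analysis.** Statistical methods puts symptom severity into a one-way repeated measures ANOVA over the four visits (aim 2). Existence of Long COVID goes into a logistic regression and severity into a linear regression (aim 3). No rule says how to treat ratings taken during or after a new infection. Limitations does not mention reinfection.

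**The concern.** The study draws a line at 4 weeks between acute COVID-19 and Long COVID, but applies it only once, at entry. Someone reinfected two weeks before the 9-month visit is in the state that would have barred entry. That person's rating is nevertheless analysed as a 9-month rating after the first diagnosis. The EORTC questionnaires cannot tell the two apart, because they rate fatigue, cough, dyspnea and similar symptoms without asking for a cause.

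Two results are exposed. The aim 2 trajectory would mix persistent symptoms with new acute ones. In aim 3, some people would be classed as having Long COVID, or given a higher severity, because of a recent infection and not because of the predictors under study. After a reinfection, time since the first diagnosis is also no longer time since the most recent infection.

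**Working it through.** **The plan's own figures.** The plan states nothing about reinfection, so there is no figure of that kind to reproduce. Its sample size matters only for the cost of the fix. An F test of R² = 0 with f² = 0.15, 6 predictors and α = 0.05 gives power 0.8035 at N = 98 and 0.7984 at N = 97, so 98 reproduces.

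**Which category the visits fall in.** Three months is about 52/4 = 13 weeks. At nominal timing every T1-T4 rating is beyond 12 weeks, so the clause on alternative diagnoses applies to all of them. Methods does not turn it into a rule.

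**How many ratings are affected.** Let a be the annual reinfection rate, assumed to be 5% to 30% and constant.

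| Quantity | Formula | a = 5% | a = 30% |
|---|---|---|---|
| Visits within 4 weeks of a new infection | a × 4/52 | 0.38% | 2.3% |
| Participants with such a visit, three visits | 1 − (1 − a × 4/52)³ | 1.2% | 6.8% |
| Participants with such a visit, four visits | 1 − (1 − a × 4/52)⁴ | 1.5% | 8.9% |
| Reinfected by month 12 (11 months at risk) | 1 − (1 − a)^(11/12) | 4.6% | 27.9% |

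The three-visit row is for people who join too late for the 3-month visit. For 98 people with four visits each (392 ratings), the first row is about 1.5 to 9 ratings.

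The table uses a as a rate in the first three rows and as an annual probability in the last. At 30% the matching rate is −ln(0.70) = 0.357, which gives 1 − exp(−0.357 × 4/52) = 2.7% instead of 2.3%. This is small beside the width of the assumed range.

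**Pattern over visits.** The first row contains no visit number. At a constant rate the acute share is the same at each visit, and only the cumulative share in the last row grows.

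**Effect on prevalence.** Take true prevalence p = 30% (the lower end of the 30-40% that the introduction gives at 6 months) and assume that 80% of those recently reinfected report symptoms. The added prevalence from acute ratings is (1 − p) × share × 0.8. That is 0.7 × 0.0038 × 0.8 = 0.2 percentage points at a = 5%, and 0.7 × 0.023 × 0.8 = 1.3 points at a = 30%.

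**Precision cost of censoring.** If 5%, 10%, 20% or 30% of the 98 are set aside for reinfection, 93, 88, 78 or 68 remain. Power at f² = 0.15 is then 0.777, 0.747, 0.680 or 0.602.

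**The case against.** - **The definition already excludes other causes.** The adopted wording rules out symptoms with an alternative explanation, and infection episodes and new diagnoses are collected at the same visits. This stands in part: the definition is sound and much of the information is gathered. But the clause sits only in the background, and existence of Long COVID has no operational definition in Methods.
- **Silence is not a rule.** Nothing says that such ratings must count as Long COVID. A reader might infer that the plan deliberately contradicts its own definition. The documents do not support that: the ratings enter because nothing removes them.
- **Aim 2 may be meant as plain description.** Symptoms and HRQOL at fixed times after diagnosis, whatever happens in between, is a legitimate target. That is a good reason to report an analysis with all ratings kept. It does not make those ratings Long COVID.
- **No upward bend is shown.** A reader might infer that the error grows with follow-up and lifts the curve at 9 and 12 months. The acute share is flat at a constant rate. Recruitment spans two quarters, with entry up to six months after diagnosis, so a calendar wave would reach different people at different visits. Cumulative reinfection does grow, but nothing in the documents shows that it affects ratings beyond the acute weeks. Counting 80% of everyone ever reinfected as symptomatic would raise a 30% prevalence to 32.8% at 5% reinfected and to 41.2% at 20%. This needs symptoms to last however long ago the reinfection was, which is unsourced.
- **The recorded episodes may not be COVID-19.** The indicator is undefined and may cover any infection. This stands, so type is needed as well as date.
- **Removal conditions on an outcome.** Infection episodes are a dependent variable, and the introduction mentions reduced immunity among long-term findings. Setting ratings aside is therefore not neutral. It should be limited to the acute window and checked against the analysis with all ratings kept.
- **A missing rating can remove a person.** A complete-case repeated measures ANOVA would drop anyone with one rating set aside. This also stands, and bears on the choice of model.

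**Conclusion.** The gap is real and of low priority. The 4-week line and the clause on alternative diagnoses are both adopted, and neither is carried into the follow-up analyses. Under the assumed 5-30% per year, the directly affected ratings are few: 0.4-2.3% of visits, and up to about 9% of participants with at least one. Acute ratings would then move prevalence by roughly 0.2 to 1.3 percentage points under the further assumptions of 30% true prevalence and 80% symptomatic. The 5-28% reinfected by month 12 is the larger number, but its effect on ratings is unknown. The size rests wholly on assumed rates. It is small if reinfection is rare and could matter if a wave falls within follow-up. Neither a direction for the trajectory nor an intended breach of the definition can be concluded.

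**What to change.** 1. Record the type and date of each infection episode reported at a visit.
2. In the aim 2 and aim 3 analyses of severity and existence, set aside ratings taken within 4 weeks of a new COVID-19 infection, matching the entry rule.
3. Analyse aim 2 with a repeated-measures mixed model in place of the one-way ANOVA, so that one missing rating does not remove the participant.
4. Report two sensitivity analyses: (a) all ratings kept, and (b) each participant censored at first reinfection.
5. Keep infection episodes as a reported outcome.

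**Cost.** One or two extra fields at contacts that are already planned. The main analysis loses about 1.5 to 9 of 392 ratings under the assumed rates. The censored analysis loses more, as the power figures show, which is why it belongs among the sensitivity analyses. No visit is added or moved.

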**Using mixed-methods approach to explore the long-term
effects of COVID-19: presentations, associating factors, and
survivor experience**

NCT ID:_____ not yet assigned _____

Last update:12/02/2021 Version5

Abstract

Background. When the COVID-19 pandemic sustains for more than a year, a growing number of COVID-19 survivors have returned to their community. However, researchers warned that up to 80% of the survivors may experience multiple and severe long-term symptoms, sometimes called Long COVID, even they were asymptomatic or only had mild symptoms at diagnosis. These Long COVID can persist for longer than three months and cause profound distress and life interferences. Findings from studies and patient reports on social media suggest that various symptoms may be experienced, including fatigue, neurological symptoms, respiratory symptoms, and cardiovascular symptoms. With that being said, more areas, such as how Long COVID evolved after diagnosis, how we identify risk groups, and what are these survivors' needs, remain unclear. **Aim.** The overarching goal of this research project is to investigate the presentations and associating factors regarding Long COVID, and to explore survivor experience. The specific aims are to (1) integrate the state of science of Long COVID, (2) describe the changes of various symptoms and HRQOL after 3, 6, 9, and 12 months of COVID-19 diagnosis, (3) explore predicting factors of the existence and severity of Long COVID, and (4) explore how patient experienced COVID-19 symptoms. **Design.** It is a mixed-methods research project with embedded design. Among the three research stages, a systematical review will be conducted first to address aim one. In stage two, a longitudinal cohort study will be carried out to recruit and follow up with individuals diagnosed with COVID-19 for a year. During the follow-up, the participants will need to report their symptoms via online questionnaire, phone or video interviews (aim 2 and 3). Those who did experience COVID-19 symptoms will be invited to join stage three study. Stage three is a qualitative descriptive study addressing aim 4. **Participants and recruitment.** For stage two, the inclusion criteria are individuals who (1) are at least 20 years-old and (2) were diagnosed with COVID-19 within six months. Individuals who have cognitive impairment or other issues that prevents them from doing self-ratings of symptoms will be excluded. Potential participants will be identified through recruitment messages posting on social media and referrals from collaborating healthcare providers. **Expecting outcomes.** It is expected that Long COVID will pose huge burden on survivors and their families. This project can provide a solid reference to foresee possible problems in this population and formulate strategies for early detection and management. It is one of the few, if there is any, longitudinal study following up with COVID-19 survivors and including patients' perspectives.

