Rather than just respiratory or localized symptoms, Long COVID seem to be more systematic [3, 4, 6]. The most frequent reported long-term symptoms across studies include fatigue (22-72%), respiratory symptoms (19-65.6%), neurological symptoms (7.2-44%), joint pain (15-19%), and psychological symptoms (4.4-46.9%) [3, 4, 6, 9]. Cardiovascular symptoms and GI symptoms were also reported [3, 4]. As studies surveyed Long COVID at different time points (from 3 weeks to 6 months) in various populations (e.g., hospitalized patients, individuals with mild, moderate, or severe acute symptoms), the incidence rate of Long COVID is between 20%-80% [3, 4, 6, 9].

While it seems that the symptoms gradually subsided over time [10], as

high as 30-40% of COVID survivors still experienced multiple symptoms at 6 months after diagnosis [4]. More importantly, these symptoms can be very frustrating. Although there is very little qualitative study described these survivors' experience or studies measured the intensity or distressing level of the persistent symptoms, some survivors have shared their horrible experience on internet [11, 12]. A 31-year-old female survivor commented that "nearly 12 months after I was first ill...I wanted to get out but I stood up and was so dizzy and breathless and so I couldn't even get dressed. [11]" Among few studies addressed health-related quality of life (HRQOL) in this population, their findings showed a significant drop in HRQOL, including impaired ability to perform daily activities, for a considerable number of COVID survivors [5, 6, 13].

In addition to the symptoms, findings from studies showed objective evidence of organ damage weeks to months after diagnosis. For example, abnormal chest x-ray, echocardiograms, elevated d-dimer, raised CRP, and lymphopenia were found and suggested lung and heart damage, clotting disorder, continuous inflammation, and reduced immunity [3, 14].

Predictors of Long COVID?

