Statistical methods. In addition to use descriptive statistics to describe the characteristics of participants and symptoms, one-way repeated measures analysis of variance (ANOVA) will be employed to determine whether there are any differences of symptom severity along the four time points (aim 2). Binomial logistic regression will be selected to predict a dichotomous dependent variable (i.e., existence of Long COVID) given multiple independent variables. Multiple linear regression will be used to predict continuous dependent variable (i.e., symptom severity) given multiple independent variables (aim 3).

Table 1. Long COVID Symptoms Mentioned by Example Studies and Instruments

First Author of the Studies or Instrument	Lopez-Leon	Romero-Duarte	EORTC-QLQ30	LC29
Fatigue	58%	22-34%	V	-
Pain	11%	-	V	V
Joint pain/ muscular pain	19%	15.3%	-	V
Muscle weakness	-	3.8%	-	V*
Weight loss	17%	-	-	V
Alopecia	25%	3%	-	V
Red eyes	6%	-	-	V
Cutaneous signs	12%	1.5-3.1%	-	V
Dyspnea	24%	28%	V	V
Polypnea	21%	-	-	V
Cough	19%	19.2%	-	V
Throat pain	3%	8.4%	-	V
Chest discomfort	16%	6.6%	-	V
Rib pain	-	4.5%	-	V
Headache	44%	5.3%	-	V*
Anosmia/ loss of the sense of smell	21%	-	-	-
Ageusia/ loss of the sense of taste/ dysgeusia	23%	7.2%	-	-
Paresthesia	-	3.4%	-	V
Attention disorder	27%	-	V	-
Memory loss	16%	-	V	-
Dizziness	3%	1.9%	-	V
Depression	12%	4.4%	V	-
Anxiety	13%	6.8%	V	-
Mood disorder	2%	-	V	-
Dysphoria	2%	-	-	-
Sleep disorder	11%	4.9%	V	-
Palpitation	11%	3.1%	-	-
Diarrhea	-	10.3%	V	
Constipation	-	1.8%	V	-
Abdomen pain	16%	5.4%	-	V*
N/v	58%	2%	V	-
Anorexia	11%	1%	V	-

Note. Table 1 compares the Long COVID symptoms mentioned by example studies and selected instruments. The percentage represents how many people have reported specific symptoms in the study. The check mark represents symptoms addressed in the instrument. Grey shading highlights symptoms that are not covered by EORTC QLQ30 or LC29. The instrument uses different terminology to describe the symptom.

Qualitative strand

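### Tying eligibility to self-rating by phone shuts out people whom another study mode could measure, and can select on the cognitive outcome

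*Combined protocol and SAP*

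**What the plan says.** Under Sampling and Recruitments (Phase two: Quantitative strand), entry is open to adults "diagnosed with COVID-19 within six months". Exclusion (1) bars anyone diagnosed less than four weeks earlier, so eligibility is judged between 4 weeks and 6 months after diagnosis. Exclusion (2) removes those who "have cognitive impairment or other issues that prevents them from doing self-ratings of symptoms via phone interviews".

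The Abstract gives the same exclusion without a mode: "Individuals who have cognitive impairment or other issues that prevents them from doing self-ratings of symptoms will be excluded". The procedures under Sampling and Recruitments are also wider than the phone: "All data collection will be occurred via online questionnaire, phone or video call interview".

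On the outcome, the Aims state: "we intend to investigate both ongoing and post-COVID-19 syndrome defined by NICE guideline and referred these symptoms as Long COVID". The guideline section places the ongoing phase at 4 to 12 weeks and post-COVID-19 syndrome after 12 weeks. The quantitative strand makes the existence and severity of these symptoms the dependent variables. Table 1 includes "Attention disorder" (27% in the cited systematic review) and memory loss (16%), both marked as covered by the QLQ-C30.

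The plan describes no proxy rating, no count of people removed by exclusion (2), and no sensitivity analysis for them. The Limitations section does not mention the exclusion.

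**The concern.** There are two linked problems.

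1. **The phone condition is narrower than the study's own methods.** A person who cannot rate symptoms in a phone interview but could do so online or by video can be refused under exclusion (2), although the study could measure that person.
2. **The criterion can act on the outcome.** The whole entry window lies inside the period that the protocol calls Long COVID. The criterion does not separate impairment that predates COVID-19 from impairment that followed it. Someone can therefore be refused because of a symptom that the study sets out to describe.

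At stake are the reported frequencies of attention and memory problems and of Long COVID overall (aim 2), and the upper end of the severity scale in the linear regressions (aim 3). The enrolled data cannot show the loss, because those concerned never enter. The qualitative strand cannot recover them either, since it recruits from phase-two participants.

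**Working it through.** **The plan's own figure.** The plan gives no number for people removed by exclusion (2). The calculated figure in the same section, 98 subjects, is reproduced: for the F test of R² = 0 with f² = 0.15, alpha 0.05 and 6 predictors, power is 0.8035 at N = 98 and 0.798 at N = 97. It does not depend on this criterion.

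**Timing.** Entry runs from 4 weeks to 6 months. Long COVID as defined runs from 4 weeks onward. The overlap is complete, so no eligibility decision precedes the outcome period.

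**Effect on a symptom frequency.** Let p be the frequency in the source population, x the share of affected people excluded and y the share of unaffected people excluded. The observed frequency is

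p(1−x) / [p(1−x) + (1−p)(1−y)].

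It falls below p only if x exceeds y. With y = 0 it becomes p(1−x)/(1−px). Take p from Table 1. The values of x are assumptions, because the documents give none.

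| Assumed x | Attention disorder, p = 27% | Memory loss, p = 16% |
|---|---|---|
| 5% | 26.0% | 15.3% |
| 10% | 25.0% | 14.6% |
| 25% | 21.7% | 12.5% |
| 50% | 15.6% | 8.7% |

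Example: 0.27 × 0.75 / (1 − 0.27 × 0.25) = 0.2025/0.9325 = 21.7%.

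For scale, the standard error of a 27% frequency in 98 people is √(0.27 × 0.73/98) = 4.5 points. The shift is 1.0 point at x = 5% and 5.3 points at x = 25%.

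**Effect on overall Long COVID frequency.** If a share q of the source population is excluded and all of them are cases, the observed frequency is (p−q)/(1−q). Take p from the 20%–80% range in the background, with 50% between, and q from 1% to 10% (assumed). Then 20% becomes 19.2% to 11.1%, 50% becomes 49.5% to 44.4%, and 80% becomes 79.8% to 77.8%.

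**Effect on odds ratios (planned logistic regression).** In any predictor group the observed odds are the true odds times (1−x)/(1−y). If x and y are the same in all groups, this factor cancels and the odds ratio is unchanged. If y = 0 and x differs between two groups, the observed odds ratio is the true one times (1−x₁)/(1−x₀). With assumed shares of 25% and 5% the factor is 0.75/0.95 = 0.79; with the shares reversed it is 0.95/0.75 = 1.27. The bias can go either way.

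**Effect on severity regressions.** If those excluded would have scored high on the cognitive scales, the severity outcome is cut at its upper end. Truncation of that kind can weaken slopes, but the documents do not allow the size to be worked out.

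**The case against.** The study rests on self-rating, and people who cannot rate themselves have no obtainable score, so some such criterion is needed. That stands, and the fix keeps it.

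The phone wording may be a slip, since the Abstract omits it and other modes are allowed. The documents give no reason why cognitive impairment would block a phone interview but not an online form. This limits the likely number affected. But the criterion also covers other issues, and as written it is what a screener would apply.

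Recruitment through hospital searches, social media and referrals gives no defined denominator, and aim 2 concerns change over time. Reported frequencies are therefore not clean population prevalences in any case. That is fair, but it is no reason to add an avoidable selection.

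The protocol calls the tabulated symptoms self-perceived, so few of the people behind the 27% and 16% may be unable to self-rate. This also stands: small values of x are plausible, and at 5% the shift is about one point or less.

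A reader might infer more than the documents support:
- *Everyone with cognitive impairment is excluded.* No: only impairment that prevents self-rating counts.
- *The worst neurological cases are lost.* Headache, paresthesia or dizziness exclude nobody unless they prevent self-rating.
- *Those excluded are by definition the most severe Long COVID cases.* The criterion also catches impairment that predates COVID-19 and unrelated issues.
- *Every predictor in aim 3 is attenuated.* A constant exclusion share leaves odds ratios unchanged.

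**Conclusion.** The point holds in a limited form. Exclusion (2) is narrower than the study's data-collection methods and differs from the Abstract. Because it is applied inside the outcome window, it can select on the outcome. Cognitive-symptom frequencies would tend to be understated. This assumes that affected people are excluded more often than unaffected people and would still have had the symptom at follow-up. The size is unknown: the tabulated shifts rest wholly on assumed shares, with cited-review figures standing in for the source population. Severity regressions may be truncated; odds ratios are biased only if exclusion shares vary across predictor levels. The sample size is unaffected. The change is worth making because it is nearly free and without a count nobody can tell whether the effect is negligible.

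**What to change.** 1. In the Abstract and in Sampling and Recruitments, reword exclusion (2) to: *cognitive impairment, or any other issue, that makes self-rating impossible by every study mode (online, phone, video)*. Do not add a blanket exclusion of pre-existing impairment, which would newly remove people with mild prior impairment who can self-rate. Screening is itself done by phone, so allow another mode there when the phone is the obstacle.
2. At screening, record the number excluded under this criterion and whether the impairment began before or after COVID-19.
3. Report cognitive-symptom and Long COVID frequencies twice: a/n among those enrolled, and (a+k)/(n+k), where a is the number affected, n the number enrolled and k the number excluded with onset after COVID-19, all counted as affected.
4. Add the exclusion to the Limitations.

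The cost is one screening-log line, a few longer contacts and a frequency reported as a range. People who never reach screening remain uncounted, so the range is not a full bound for the source population.

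### The recruitment target of 118 is too small for the plan's own 20% loss: it leaves 94 subjects, not the required 98, and the target should be 123.

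*Combined protocol and SAP*

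**What the plan says.** The sample size is set in the combined protocol and SAP, under Phase two: Quantitative strand, Sampling and Recruitments. The base number is given as "The estimated sample size is about 98 subjects based on G*Power 3.1.9.4 calculation", with the inputs "effect size $f^2=0.15$, $\alpha=0.05$, $\beta=0.2$, 6 predictors". The next sentence gives the recruitment target: "Considering the loss of follow-up rate of 20%, 118 subjects are needed".

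The paragraph names neither the G*Power test nor the formula used to allow for loss. An effect size f² with a predictor count fits the multiple linear regression of symptom severity that the Statistical methods paragraph plans for aim 3. No other section gives a second target or a further allowance. The Limitations section says that a one-year follow-up makes retention difficult and lists measures to improve it, but gives no figures.

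**The concern.** A loss to follow-up rate is a proportion of the people enrolled. To finish with a given number, that number must be divided by the proportion retained. Multiplying it by one plus the loss rate takes the percentage of the wrong base and always gives too few. The stated 118 is what the multiplication gives.

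This is the only sample size calculation for the quantitative strand, which the Methods section calls the main part of the project, and 118 is the number at which recruitment would stop. As the timeline in Table 4 reads, recruitment ends well before data collection does, so a shortfall seen late in follow-up could not be made up by enrolling more people. The error also goes in the unfavourable direction: if loss is what the plan expects, the planned power is not reached.

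**Working it through.** **Inputs**, all from Sampling and Recruitments: f² = 0.15, α = 0.05, β = 0.2 (power 0.80), 6 predictors, required N = 98, loss 20%, target 118.

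**Step 1. Reproduce the 98.** For the overall F test in multiple linear regression, the noncentrality is λ = f² × N, with 6 and N − 7 degrees of freedom. Power is the probability that a noncentral F variable exceeds the 5% critical value.

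| N | Power |
|---|---|
| 97 | 0.7984 |
| 98 | 0.8035 |

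So 98 is exactly the smallest N that reaches 0.80. A t test of a single coefficient with the same inputs would need 43 (one-sided) or 55 (two-sided), so it does not explain 98. The base figure is correct and has no slack: 97 already falls below 0.80.

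**Step 2. Reproduce the 118.** Two ways of allowing for 20% loss:

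- 98 × (1 + 0.20) = 117.6, rounded up to 118. This is the stated target.
- 98 / (1 − 0.20) = 122.5, rounded up to 123. This is not the stated target, and a gap of 5 is too large to be rounding.

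**Step 3. Apply the plan's own loss rate to 118.** 118 × 0.80 = 94.4, so 94 remain, which is 98 − 94 = 4 short. Power at N = 94 is 0.7824.

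**Step 4. Find the loss that 118 can absorb.** 1 − 98/118 = 20/118 = 0.169. The target holds only if no more than 20 of the 118 are lost, or 16.9%.

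**Step 5. Check the corrected target.** 123 × 0.80 = 98.4, so 98 remain and power is 0.8035.

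**The case against.** The arithmetic is hard to dispute; the case on the other side concerns how much it matters and how far it reaches.

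- **Size.** The loss is under two points of power. With 94 subjects the test has 80% power at f² = 0.156 instead of 0.15. As R² = f²/(1 + f²), that is 0.135 instead of 0.130. The plan gives no source for f² = 0.15 or for the 20% loss, and both are less certain than this difference. This stands: no conclusion of the study is likely to turn on it.
- **The formula is inferred.** The plan does not say that it multiplied by 1.2. This stands, but the finding does not depend on it: 118 less 20% is below 98 however 118 was reached.
- **Who is analysed.** The Statistical methods paragraph does not say which visit supplies the regression outcome, and the plan does not say by which visit the 20% is lost. A regression at 6 or 9 months might include more than 94 subjects. At 3 months there may be fewer for a different reason, since only those enrolled within three months of diagnosis have that visit. This stands as a condition on the 94 and the 78.2%.
- **Scope.** The calculation fits only the linear regression. The repeated-measures ANOVA and the logistic regression carry no power statement, and the aims are to describe and explore. This stands too: the shortfall concerns one of the planned analyses.

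None of these points makes 118 sufficient for 98 subjects at 20% loss.

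**Conclusion.** The concern holds. At the plan's own 20% loss, 118 enrolled subjects do not give the plan's own 98; the number that does is 123, five more than stated. The consequence is modest: 94 subjects and 78.2% power against a planned 80%.

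The conclusion that 118 is too few needs only the stated figures and the ordinary reading of loss to follow-up as a share of those enrolled. The power figures further assume that the calculation is for the overall F test in linear regression, which reproduces 98 exactly, and that the full 20% is lost by the visit analysed. The study is not undermined, but a planning figure that it relies on is wrong as written and should be corrected.

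**What to change.** Change the sentence in Sampling and Recruitments in one of these ways, and show the formula:

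1. **Correct the target.** State that 123 subjects are needed (98 / 0.80 = 122.5, rounded up). This costs five more participants within the planned recruitment period.
2. **Keep 118 and restate the loss.** State that 118 allows for a loss of up to 16.9%, that is 20 of 118 subjects. This costs nothing in recruitment, but the lower loss rate would then need to be defended.
3. **Keep 118 and 20%, and restate the power.** State that 94 subjects are expected to remain, with 78% power for f² = 0.15. This costs nothing beyond accepting the lower power.

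Whichever is chosen, name the test behind the calculation and the visit to which the 20% loss refers, so that the figure can be checked.
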